## Cohorts A and B

Individual values will be listed for each PK parameter by treatment, and the following (nonmodel-based) descriptive statistics will be provided: N (number of subjects with nonmissing data), arithmetic mean, standard deviation, arithmetic percent coefficient of variation (CV) (calculated as  $100 \times \text{standard deviation}/\text{arithmetic mean}$ ), median, minimum, maximum, geometric mean, and geometric percent CV (calculated as  $100 \times \sqrt{\exp(s^2) - 1}$ ), where  $s^2$  is the observed variance on the natural log-scale).

### 9.6.2 Statistical Methods for Efficacy Analyses (Cohort B)

This section describes the statistical methods that address the primary and secondary objectives.

#### 9.6.2.1 Objective Response Rate (ORR)

ORR will be calculated as the ratio of the number of participants reported to have achieved a confirmed CR or PR verified by BICR, divided by the number of participants included in APaT population. Participants in the APaT analysis population without ORR assessments will be counted as non-responders.

A 95% exact binomial CI (based on method Clopper and Pearson,1934) will be calculated for the true ORR.

### 9.6.2.2 Progression-free Survival (PFS)

The non-parametric Kaplan-Meier method will be used to estimate the PFS distribution. 95% CIs for the median PFS and PFS point estimates at various follow-up times from first day of study treatment will be calculated.

Since disease progression is assessed periodically, PD can occur any time in the time interval between the last assessment where PD was not documented and the assessment when PD is documented. The true date of PD will be approximated by the date of the first assessment at which PD is objectively documented based on RECIST 1.1 by BICR. Death is always considered as a PFS event. Participants who do not experience a PFS event will be censored at the last disease assessment.

For the analysis of PFS, if the events (PD or death) are immediately after more than one missed disease assessment, the data are censored at the last disease assessment prior to missing visits. Also, data after new anticancer therapy are censored at the last disease assessment prior to the initiation of new anticancer therapy. The censoring rule is summarized in [Table 10](#). If a participant meets multiple criteria for censoring, the censoring criterion that occurs earliest will be applied.

Table 10 Censoring Rules for Analysis of Progression-free Survival

Situation	Date of Progression or Censoring
PD or death documented after $\leq 1$ missed disease assessment, and before new anticancer therapy, if any	Progressed at date of documented PD or death
PD or death documented immediately after $\geq 2$ consecutive missed disease assessments or after new anticancer therapy, if any	Censored at last disease assessment prior to the earlier date of $\geq 2$ consecutive missed disease assessment and new anticancer therapy, if any
No PD and no death; and new anticancer treatment is not initiated	Censored at last disease assessment
No PD and no death; new anticancer treatment is initiated	Censored at last disease assessment before new anticancer treatment
Abbreviations: PD=progressive disease; PFS=progression-free survival	

### 9.6.2.3 Overall Survival (OS)

The non-parametric Kaplan-Meier method will be used to estimate the OS distribution. 95% CIs for the median OS and OS point estimates at various follow-up times from first day of study treatment will be calculated.

#### 9.6.2.4 Duration of Response (DOR)

DOR will be summarized descriptively using the non-parametric Kaplan-Meier method. Only the subset of participants who show a CR or PR will be included in this analysis. Censoring rules for DOR are summarized in [Table 11](#).

Table 11 Censoring Rules for Duration of Response

Situation	Date of Progression or Censoring	Outcome
No progression nor death, no new anticancer therapy initiated	Last adequate disease assessment	Censor (non-event)
No progression nor death, new anticancer therapy initiated	Last adequate disease assessment before new anti-cancer therapy initiated	Censor (non-event)
Death or progression immediately after $\geq 2$ consecutive missed disease assessments or after new anti-cancer therapy, if any	Earlier date of last adequate disease assessment prior to $\geq 2$ missed adequate disease assessments and new anti-cancer therapy, if any	Censor (non-event)
Death or progression after $\leq 1$ missed disease assessments and before new anti-cancer therapy, if any	Progressive disease or death	End of response (Event)
Note: A missed disease assessment includes any assessment that is not obtained or is considered inadequate for evaluation of response. DOR = duration of response		

#### 9.6.2.5 Analysis Strategy for Key Efficacy Endpoint

[Table 12](#) summarizes the primary analysis approach for key efficacy endpoints.

Table 12 Analysis Strategy for Key Efficacy Endpoints

Endpoint	Statistical Method a	Analysis Population	Missing Data Approach
Primary Endpoints			
ORR per RECIST 1.1 by BICR	Exact method based on binomial distribution (Clopper-Pearson method)	APaT	Participants without assessments are considered non-responders and conservatively included in the denominator
Key Secondary Endpoint			
PFS per RECIST 1.1 by BICR	Summary statistics using Kaplan-Meier method	APaT	
 
• Primary censoring rule
 
• Sensitivity analysis 1
 
• Sensitivity analysis 2
 
 (More details are provided in Table 10 , Censoring Rules for Primary and Sensitivity Analyses of PFS)
OS	Summary statistics using Kaplan-Meier method	APaT	Censored at the last known alive date
DOR per RECIST 1.1 by BICR	Summary statistics using Kaplan-Meier method	APaT	Non-responders are excluded from analysis. Responders are censored according to the censoring rules listed in Table 11 .
a Statistical models are described in further detail in the text. Abbreviations: APaT=All Participants as Treated; BICR=blinded independent central review; DOR=duration of response; ORR=objective response rate; OS=overall survival; PFS=progression-free survival; RECIST=Response Evaluation Criteria in Solid Tumors			

### 9.6.3 Statistical Methods for Safety Analysis (Cohort A)

Safety and tolerability will be assessed by clinical review of all relevant parameters including AEs, SAEs, laboratory tests, vital signs, and physical examinations.

#### Cycles 1 through 3

The counts and frequency of AEs including injection site reaction AEs will be summarized by treatment and by sequence. In addition, AEs will be summarized based on Treatment Cycle 1 data only as well. Laboratory tests, vital signs, and other safety endpoints will be summarized as appropriate.

Descriptive summary statistics will be provided for the injection site signs and symptoms questionnaire data by treatment.

### Post Cycle 3

Adverse events collected from Cycle 4 to the end of the study will reported.

#### **9.6.4 Statistical Methods for Safety Analyses (Cohort B)**

Safety and tolerability will be assessed by clinical review of all relevant parameters including adverse experiences and laboratory parameters.

The broad AE categories consisting of the percentage of participants with any AE, a drug-related AE, a serious AE, an AE which is both drug-related and serious, and who discontinued due to an AE will be summarized via point estimates with 95% CIs (Table 13).

Table 13 Analysis Strategy for Safety Parameters

Safety Endpoint	Within Group 95% CI	Descriptive Statistics
Any AE	X	X
Any Serious AE	X	X
Any Drug-related AE	X	X
Any Serious and Drug-related AE	X	X
Discontinuation due to AE	X	X
Specific AEs, SOCs, or PDLCs		X
Change from Baseline Results (Labs, Vital Signs)		X
Note: 95% CIs will be calculated using the Clopper Pearson method X = results will be provided Abbreviations: SOC=System Organ Class; PDLC=Pre-Defined Limit of Change		

For continuous measures such as changes from baseline in laboratory parameters, summary statistics for baseline, on-treatment, and change from baseline values will be provided in table format.

#### **9.6.5 Demographics and Baseline Characteristics (Cohort B)**

The number and percentage of subjects screened, allocated, the primary reasons for screening failure, and the primary reasons for discontinuation will be displayed. Demographic variables (e.g., age, gender), baseline characteristics, primary and secondary diagnoses, and prior and concomitant therapies will be summarized either by descriptive statistics or categorical tables for all enrolled subjects.

### **9.7 Interim Analyses**

No interim analysis is planned.

## 9.8 Multiplicity

No multiplicity adjustment is planned for this study.

## 9.9 Sample Size and Power Calculations

### Cohort A

The overall sample size for this Phase 1 study is expected to be up to approximately 30 to 36 participants. Assuming that the within-subject standard deviation of pembrolizumab AUC in melanoma patients following subcutaneous administration is the same as it is following IV administration (which is 0.25 on log scale based on previous pembrolizumab studies) and assuming the true GMR of AUC between SC injection and IV infusion is 1.0, with 30 completers the 90% CI of GMR will be (0.90, 1.11).

A between-subject comparison will also be provided based on Treatment Cycle 1 data only. The between-subject standard deviation of pembrolizumab AUC in melanoma patients following IV administration is 0.30 on log scale based on previous pembrolizumab studies. Assuming the between-subject standard deviation following SC administration is 0.50 on log scale based on published SC PK data for other mAbs [Dirks, N. L. 2010], when the true GMR of AUC between SC injection and IV infusion is 1.0, with 10 completers in each treatment (30 in total), the 90% CI of GMR will be (0.72, 1.38).

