## **9 STATISTICAL ANALYSIS PLAN**

### **9.1 Statistical Analysis Plan Summary**

This section outlines the statistical analysis strategies and procedures for the primary, secondary, and exploratory analyses of the study.

If, after the study has begun, changes are made to primary and/or secondary objectives, or the statistical methods related to those objectives, then the protocol will be amended (consistent with ICH Guideline E9). Post hoc exploratory analyses will be clearly identified in the Clinical Study Report (CSR).

Full details are in the Statistical Analysis Plan, Section 9.2 through Section 9.12.

Study Design Overview	Phase 1, relative bioavailability, cross-over study of pembrolizumab administered via IV infusion or SC injection in participants with advanced melanoma (Cohort A) and of IV pembrolizumab Q6W dosing (Cohort B).
Treatment Assignment	
In Cohort A, participants will be randomized to 1 of 6 treatment arms and will receive 1 IV infusion and 2 SC injections over the first 3 cycles, followed by IV infusion of pembrolizumab for up to 35 cycles.
 
In Cohort B, participants will receive IV infusion of pembrolizumab Q6W for up to 18 cycles.
 
Enrollment into Cohort A takes priority over Cohort B.

Analysis Populations	
Cohort A:
 
PK (Primary): Per-Protocol (PP)
 
Safety (Secondary): All-Participants-as-Treated (APaT)
 
Cohort B:
 
Efficacy (Primary): Full Analysis Set (FAS)
 
PK (Secondary): Per-Protocol (PP)
 
Safety (Secondary): All-Participants-as-Treated (APaT)

Primary Endpoint(s)	
Cohort A: Pharmacokinetic parameters of pembrolizumab, including area under the curve (AUC), maximum concentration (<math>C_{max}</math>), bioavailability (F), absorption rate (Ka), time of maximum concentration (<math>T_{max}</math>), clearance (CL), and central volume of distribution (Vc)
 
Cohort B: ORR per RECIST 1.1. by BICR

Secondary Endpoints	
Cohort A:
 
 
• Circulating antidrug antibody levels
 
• Adverse events (AEs)
 
• Discontinuing study treatment due to an AE
 
• Responses to the injection site signs and symptoms questionnaire
 
 
Cohort B:
 
 
• DOR per RECIST 1.1 by BICR
 
• PFS per RECIST 1.1 by BICR
 

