	
 
• OS
 
• Adverse events (AEs)
 
• Pharmacokinetics: Pharmacokinetic parameters of pembrolizumab, including AUC, Cmax, and Cmin after administration of 400 mg Q6W pembrolizumab
 

Exploratory	Cohort B 
 
• Circulating antidrug antibody levels
 

Statistical Methods for Pharmacokinetic Analyses	Cohort A: The relative bioavailability of pembrolizumab via SC injection will be estimated using AUC comparing with that via IV infusion. The log-transformed AUC of pembrolizumab will be analyzed with a linear mixed effects model with fixed effects terms for treatment and cycle. Point estimates for Geometric Mean Ratio (GMR, SC CCI versus IV, SC CCI versus IV) and their 90% confidence intervals (CIs) will also be calculated.
Statistical Methods for Safety Analyses	Summary statistics will be provided for the safety endpoints as appropriate.
Statistical Methods for Efficacy Analyses	Cohort B: Estimation of ORR; Estimation of DOR, PFS and OS using the Kaplan-Meier method.
Interim Analyses	No interim analysis is planned. Two PK analyses will be conducted during the study. The first PK analysis will occur when at least 30 participants have completed the first 3 cycles of this study in Cohort A. The second PK analysis will occur after Cycle 5 in Cohort B.
Multiplicity	No multiplicity adjustment is planned for this Phase 1 research design.
Sample Size and Power	There is no hypothesis testing. For Cohort A, assuming the true GMR of AUC between SC injection and IV infusion is 1.0, with 30 completers the 90% CI of the GMR will be (0.90, 1.11). For Cohort B, assuming the observed ORR is what is expected with pembrolizumab 200 mg Q3W for 35 cycles (~35%), 100 subjects will assure a 95% CI for the true ORR of approximately (25%, 45%).
Abbreviations: BICR=blinded independent central review; DOR=duration of response; ORR=objective response rate; OS=overall survival; PFS=progression-free survival; RECIST 1.1=Response Evaluation Criteria in Solid Tumors 1.1	

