## 9.3 Hypotheses/Estimation

Objectives of the study are outlined in Section 3.0. No hypotheses are being tested in this study.

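### The Cohort A cross-over 90% CI of (0.90, 1.11) implicitly assumes equal SC and IV between-subject variance, which conflicts with the SDs of 0.50 and 0.30 assumed in the next paragraph of Section 9.9

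*Combined protocol and SAP*

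**What the plan says.** Section 9.9 makes two precision statements for Cohort A. Both concern the SC/IV geometric mean ratio (GMR) of AUC with a true GMR of 1.0 and 30 completers.

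- **Cross-over comparison (primary).** The "within-subject standard deviation of pembrolizumab AUC in melanoma patients following subcutaneous administration is the same as it is following IV administration", given as 0.25 on the log scale. The expected 90% CI is (0.90, 1.11).
- **Cycle 1 comparison (supportive).** "A between-subject comparison will also be provided based on Treatment Cycle 1 data only". For this, "The between-subject standard deviation of pembrolizumab AUC in melanoma patients following IV administration is 0.30 on log scale", and for the other route: "Assuming the between-subject standard deviation following SC administration is 0.50 on log scale based on published SC PK data for other mAbs". With 10 completers per treatment the expected 90% CI is (0.72, 1.38).

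Section 9.1 carries forward only the first interval, without the 0.25 on which it rests, and for detail says: "Full details are in the Statistical Analysis Plan, Section 9.2 through Section 9.12". Section 9.3 states: "No hypotheses are being tested in this study". Section 9.6.1 plans a mixed model with an unstructured covariance matrix that allows the treatment variances to differ.

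**The concern.** A cross-over comparison removes between-subject variance only to the extent that each subject's effect is the same under both routes. If subjects vary more under SC than under IV, part of their effect stays in the within-subject difference as subject-by-route variance, even when the two effects are perfectly correlated. The first calculation has no such term. The second assumes SDs that require one.

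The text equates only the within-subject SDs. The equality of between-subject variances is not written; the formula behind the interval carries it.

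Relative bioavailability is a primary objective of Cohort A. Because the study only estimates, the expected CI width is the whole justification for 30 completers. If it is too favourable, a reader expects more precision than the plan's own variances support, and 9.1 gives no hint that the figure depends on an assumption contradicted in 9.9.

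**Working it through.** **Inputs from 9.9:** within-subject SD 0.25 for both routes; SDs 0.30 (IV) and 0.50 (SC); 30 completers, or 10 per treatment in Cycle 1; GMR 1.0; 90% two-sided CI, z = 1.645.

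**Assumptions not in the documents:** within-subject errors independent between cycles, and an SC–IV subject-effect correlation ρ. I use ρ = 1, the most favourable value, and vary it at the end.

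**1. The plan's cross-over CI.** Var(log SC − log IV) = 2 × 0.25² = 0.125. SE = 0.25 × √(2/30) = 0.0645.
- z gives (0.899, 1.112); t on 58 df gives (0.898, 1.114). Both match the stated (0.90, 1.11).
- t on 29 df gives (0.896, 1.116).

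**2. The plan's Cycle 1 CI.** SE = √((0.09 + 0.25)/10) = 0.184. Welch t on 14.7 df gives (0.724, 1.382), the stated (0.72, 1.38). So 0.30 and 0.50 were used here as total SDs, although they are called between-subject.

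**3. Cross-over CI with the second paragraph's SDs.** With b the between-subject SDs,

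Var = b_SC² + b_IV² − 2ρ·b_SC·b_IV + 2 × 0.25², and SE = √(Var/30).

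*Total SDs.* b_SC = √(0.25 − 0.0625) = 0.433; b_IV = √(0.09 − 0.0625) = 0.166. At ρ = 1 the subject-by-route variance is (0.433 − 0.166)² = 0.0714, so Var = 0.1964 and SE = 0.0809.

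*Purely between-subject SDs.* (0.50 − 0.30)² = 0.040, so Var = 0.165 and SE = 0.0742. On this reading the Cycle 1 calculation omits 0.0625 per arm. With it, SE = √((0.1525 + 0.3125)/10) = 0.216, and Welch t on 16.1 df gives (0.686, 1.457).

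| Case (ρ = 1) | Var | 90% CI, z | 90% CI, t on 29 df | Half-width ratio |
|---|---|---|---|---|
| As stated | 0.125 | (0.899, 1.112) | (0.896, 1.116) | 1.00 |
| Total SDs | 0.1964 | (0.875, 1.142) | (0.872, 1.147) | 1.25 |
| Between-subject SDs | 0.165 | (0.885, 1.130) | (0.882, 1.134) | 1.15 |

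As a gauge of size, matching the stated width would take 30 × 0.1964/0.125 = 47.1, so 48 completers, or 30 × 0.165/0.125 = 39.6, so 40.

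**4. Can the total-SD reading be reconciled?** A variance of 0.125 needs an SC–IV correlation of (0.34 − 0.125)/(2 × 0.50 × 0.30) = 0.717. A within-subject SD of 0.25 with independent errors allows at most 0.433 × 0.166/0.15 = 0.479.

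**5. Could correlated errors close the gap?** Restoring 0.125 needs an error correlation r of 0.0714/0.125 = 0.571 (total) or 0.040/0.125 = 0.32 (between-subject). The same r in the first paragraph's formula, 0.25 × √(2(1 − r)/30), gives SE 0.0423 and (0.933, 1.072), or SE 0.0532 and (0.916, 1.092). The two paragraphs still disagree.

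**6. Lower ρ (sensitivity, z).** ρ = 0.8 gives Var = 0.225 on either reading and (0.867, 1.153). ρ = 0.5 gives (0.856, 1.168) on total SDs or (0.845, 1.184) on between-subject SDs.

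**The case against.** The case for leaving the text alone has several parts.

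- **There is no slip in calculation.** That stands: both intervals follow from their own inputs. The fault is that the two sets of inputs are incompatible.
- **The plan equates only within-subject SDs.** Also true, which is why the finding says the equality is implicit. But (0.90, 1.11) cannot be obtained from 0.25 × √(2/30) without it.
- **The total-SD reading is a construction.** It subtracts a pembrolizumab within-subject variance from an SC value taken from other antibodies, and nothing says 0.25 applies to them. This is fair. In its favour, it is the reading that reproduces (0.72, 1.38). The literal between-subject reading gives the smaller shift, and I give both equal weight.
- **ρ = 1 and independent errors are not in the documents.** Correct. The stated formula also uses independence, which is itself open to question with a half-life of about 3 weeks (Section 2.2.2) and 21-day cycles. The carry-over adjustment in 9.6.1 enters none of these intervals. The inconsistency is firm; a particular replacement interval is conditional.
- **The analysis copes, and nothing turns on the figure.** The unstructured covariance will let the reported CI reflect subject-by-route variance, and no margin or decision rule uses the interval. This limits the consequence but does not make the planning figure in 9.9 and 9.1 consistent.

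**Conclusion.** The concern holds. The stated cross-over precision leaves no room for the SC/IV variance difference assumed one paragraph later. Even under the most favourable subject-effect correlation, with independent errors and like for like on the normal quantile, the CI is about (0.88, 1.14) for total SDs or (0.89, 1.13) for between-subject SDs. Each limit moves by 0.01 to 0.03. With independent errors, any lower subject-effect correlation widens the interval further.

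The direction does not depend on how 0.30 and 0.50 are read; the exact size does, and the documents do not settle it. The effect is confined to the precision stated for a primary estimate. Sample size, analysis model and conduct are not called into question.

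**What to change.** In 9.9, say whether 0.30 and 0.50 are total or purely between-subject SDs, and use one set of variance components for both Cohort A calculations. Then take one of two routes.

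- **Restate.** For total SDs: *assuming independent within-subject errors and an SC–IV subject-effect correlation of 1, the 90% CI (normal quantile) would be about (0.88, 1.14)*. For between-subject SDs, use the same sentence with (0.89, 1.13) and restate the Cycle 1 CI as about (0.69, 1.46), naming its Welch t quantile. Because a correlation of 1 is the best case, a figure at a lower correlation would help; 0.8 gives (0.87, 1.15) on either reading.
- **Keep and disclose.** Retain (0.90, 1.11), say in both 9.9 and 9.1 that it assumes equal SC and IV between-subject variance and no subject-by-route variance, and give the wider interval beside it.

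Either route means two or three sentences in 9.9 and one matching edit in 9.1. The cost is a slightly less favourable figure and, if the interval is restated, an explicit SC–IV subject-effect correlation that the plan does not now give.

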### Cohort B

Approximately 100 participants will be enrolled in Cohort B. The ORR for the dose and schedule to be used in Cohort B is expected to be similar to that seen with pembrolizumab, 200 mg Q3Ws 35 cycles (~ 35%). If the observed ORR for the 100 subjects was 35%, a 95% CI for the true ORR based on the method of Clopper and Pearson (1934) would be (25.7%, 45.2%).

## 9.10 Subgroup Analyses

### Cohort A

There will be no subgroup analyses conducted for Cohort A.

### Cohort B

To determine whether the response rate is consistent across various subgroups, the estimate of the response rate (with a nominal 95% CI) for the primary endpoint will be estimated within each category of the following classification variables:

- Age category (< 65 vs. ≥ 65 years)
- Sex (female vs. male)

- Race (white vs. non-white)
- Disease stage (III vs. IVM1a vs. IVM1b vs. IVM1c)
- Brain metastasis (yes vs. no)
- ECOG status (0 vs. 1)
- PD-L1 status (positive vs. negative [includes indeterminate])
- BRAF wild type versus BRAF mutant (no prior treatment) versus BRAF mutant (prior treatment)
- LDH ( $\leq$  ULN vs.  $>$  ULN but  $<$  2X ULN vs.  $\geq$  2X ULN)

A Forest plot will be produced, which provides the estimated point estimates and CIs for the treatment effect across the categories of subgroups listed above.

Any specified subgroups that have less than 10 participants will be excluded from analysis.

